1.6.3 Radiation-induced secondary tumors

Induction of neoplasms by fractionated radiotherapy for various primary diseases, like meningioma, pituitary adenoma, craniopharyngeoma, medulloblastoma, leukaemia and tinea capitis has been noted both after low and high irradiation doses. Various types of secondary tumors have been reported, such as astrocytoma, GBM, gliosarcoma, ependymoma, meningioma and outside the cranium leukaemia, lymphoma, thyroid carcinoma, peripheral fibrosarcoma. These consequences are infrequent but possible. The overall risk for radiation-induced cancers has been estimated around 2-10% for all adults treated with radiotherapy (Ref. 97).

The consensus criteria for identifying radiation induced cancers are: 1) the tumor must appear in the irradiated area, 2) the tumor was not present prior to irradiation, 3) a proper number of years latency must have elapsed between irradiation and the appearance of the tumor (usually five years or more (Ref. 98)), 4) the radiation-induced tumor must be histologically proven and must distinctly differ from the original histology, 5) there must be no concerns to a genetic multiple predisposition syndrome (Ref. 99).

1.7 Conclusions

The overall policy in the treatment of non-benign meningiomas is controversial. It usually includes aggressive surgical resection of the tumor and of its dural attachments. If complete resection of the tumor is not possible or if it is deemed to be associated with an unacceptable morbidity, surgery should be more reserved. Post-operative radiation might reduce the local tumor recurrence rate for these aggressive tumors. A dose-response relationship has been suggested by several retrospective studies although this issue is controversial. Considering the lack of prospective data and the controversy around the dose escalation issue for this tumor entity, it was decided to perform the present prospective phase II study. There is no prospective study addressing the potential local control benefit of adjuvant high-dose radiotherapy for non-benign meningiomas weighted against the potential radiation induced toxicity. Atypical (grade WHO 2) patients will be accrued in this study. A separate observation study will be initiated for malignant (grade WHO 3) meningiomas, as this tumor type is rare (see Prognostic factors in meningiomas, section 4.1.5). No dose-escalation policy is planned for malignant meningiomas.

2 Objectives of the trial

2.1 General objectives

The objectives of this study are to assess the impact of high-dose radiotherapy (RT) on progression-free survival (PFS), treatment tolerance, and post-treatment global cognitive functioning in patients with a diagnosis of either atypical (grade WHO II) or malignant (grade WHO III) meningioma.

The atypical meningioma patients will be entered in one of two strata of a non-randomized phase II study, depending on the Simpson's stage achieved by surgery. The malignant meningioma patients will be registered in a separate stratum. For the latter group, no strict statistical design is planned due to the expected small patient number.

This study is the first one assessing the value of post-operative high-dose radiotherapy in grade II and grade III meningioma patients and the results will serve as a basis for designing future studies in this disease. If the patient accrual rate is high enough and if dose escalation to 60 or 70 Gy demonstrates sufficient activity with acceptable toxicity, a phase III trial might be considered in the future.

2.2 End-points

The primary trial endpoint is progression-free survival where progression is defined on the basis of tumor growth or appearance of new lesions (see chapter 7 for exact definition).

The secondary trial endpoints are acute and late effects classified according to the National Cancer Institute Common Terminology Criteria for Adverse Events v 3.0 (NCI CTCAE v3.0), mini-mental status (MMSE) and overall survival.

Quality of life is not an endpoint in this study since the trial is not randomized and is of relatively small size.

3 Patient selection criteria

Patients will be registered between surgery and the start of radiotherapy without exceeding 6 weeks time interval.

- ◆ **Histologically proven newly diagnosed atypical grade WHO grade II meningioma** (≥ 4 mitosis per high-power field [HPF] or the presence of at least 3 of the latter 4 variables: cellularity, architectural sheeting (i.e. patternless pattern), macronuclei and small cell formation) (see section 3.2 below for definition)

OR

- ◆ **Histologically proven newly diagnosed malignant WHO grade-III meningioma** (see section 3.2 below for definition)

(as assessed by the local pathologist)

AND all of:

- ◆ Complete or subtotal resection as assessed by the surgeon after verification with a postoperative MRI and according to Simpson guidelines (see section 3.4 below for definition). The patients will be stratified according to the resection status: complete excision (Simpson's stages 1-3) versus incomplete excision (Simpson's stages 4-5)
- ◆ Age between 18 years and 70 years
- ◆ WHO performance status 0-2
- ◆ All locations except optic nerve sheath tumors
- ◆ No neurofibromatosis type II patients (NF-2)
- ◆ No previous radiotherapy to the brain or meninges interfering with the protocol treatment plan
- ◆ No clinical evidence of second malignancies, except a history of cervix carcinoma in situ and basocellular carcinoma
- ◆ Women of reproductive potential must use effective contraception for the whole duration of the treatment and must not be pregnant or lactating.
- ◆ Absence of any psychological, familial, sociological or geographical condition potentially hampering compliance with the study protocol and follow-up schedule; those conditions should be discussed with the patient before registration in the trial
- ◆ Before patient registration, written informed consent must be given according to ICH/GCP, and national/local regulations.

Patients can be registered in this trial only once.

3.1 WHO grading of meningiomas

For assessing eligibility for entry, on study, the specimens will be signed out by the pathologist at the treating institution according to the criteria of the WHO (Ref. 1). These criteria read as follows:

- ◆ WHO definition of **atypical meningioma (WHO grade II)**: a meningioma with increased mitotic activity or three or more of the following features: increased cellularity, small cells with high nucleus/cytoplasm ratio, prominent nucleoli, uninterrupted patternless or sheet-like growth, and foci of «spontaneous» or «geographic necrosis».
- ◆ WHO definition of **anaplastic (malignant) meningioma (WHO grade III)**: a meningioma exhibiting histological features of frank malignancy far in excess of the abnormalities present in atypical meningioma.

After entry on study, the diagnostic pathology will be reviewed centrally (see chapter 15.3 – Pathology review).

3.2 Simpson's guidelines for assessing resection level

The resection level will be assessed by the surgeon after verification with a postoperative MRI and will be classified according to Simpson guidelines as

Table 2. Simpson grading

Radical

Stage 1 : complete excision, including dura and bone.

Stage 2 : complete excision + supposed reliable coagulation of dural attachment.

Non-radical

Stage 3 : complete excision but insufficient dural coagulation or bone excision (non visible on MR, according to surgeon's opinion).

Stage 4 : incomplete excision, macroscopic rest visible (on MRI).

Stage 5 : biopsy only (visible on MRI).

4 Trial Design

For patients with atypical meningioma (grade II) the trial is designed as two parallel non-randomized phase-II trials with progression-free survival rate at 3-years as primary endpoint, in respectively patients with Simpson's stage 1-3 resection and patients with Simpson's stage 4-5 resection.

A separate one-stage Fleming design will be applied each to the two strata of patients. The criteria for success are respectively to demonstrate that the 3-year progression free survival is superior to 70% for patients with Simpson's stage 1-3 and that it is superior to 50% for patients with Simpson's stage 4-5.

With such a design, a total of 25 patients with Simpson stage 1-3 grade II meningiomas and 39 patients with Simpson stage 4-5 meningiomas are needed (total phase II study, 64 patients).

[figure not shown]
For the grade III meningiomas, given the small numbers expected to enter the trial, the patients will be registered only and treated and then followed-up similarly to the grade II meningiomas (see chapter 6). No specific statistical design, decision rule, or sample size is defined for this small group and only descriptive statistics will be produced.

The trial duration will be driven by the phase II study. It is foreseen that 6-13 grade-III patients will be registered during the accrual period of the phase II.

Patients need to be eligible and to have started treatment. The local pathology will be used for assessing eligibility.

Accrual to the phase II is anticipated to last 3 years.

Trial scheme:

5 Therapeutic regimens, expected toxicity, dose modifications

5.1 Guidelines for Radiotherapy (including 3DCRT, IMRT and SRT)

5.1.1 Equipment

Linear accelerator (Linac) X-ray beams with nominal energy of at least 4 MV and not greater than 20 MV should be used. Three dimensional conformal therapy (3D CRT) is mandatory. Intensity modulated radiotherapy (IMRT) and fractionated stereotactic radiotherapy (with or without IMRT) is permitted in this study.

5.1.2 Definition of target volumes

The Gross Tumor Volume (GTV) is defined as the visible tumor which is the region of enhancement on post-operative brain MRI (T1Gado+) and planning CT-scan (with iodine contrast). If bone is involved, a CT bone window (setting) is strongly advised. Clearly thickened dural trails and hyperostotic bones are as much as appropriately included; enhancing dura without being thickened is not included.

The Clinical Treatment Volume 1 (CTV1) is defined as the GTV and sub clinical microscopic tumor (may include the pre-operative tumor or post-operative tumor bed, peritumoral edema, hyperostotic changes if any, and dural enhancement or thickening as seen in the CT/MRI at diagnosis) plus a 3D 10 mm margin (in all directions but not extending outside the patient) or less (see dose constraints, chapter 5.1.7).

The CTV2 is defined as the GTV and sub clinical microscopic tumor (may include the pre-operative tumor bed, peritumoral edema, hyperostotic changes if any, and dural enhancement or thickening as seen in the CT/MRI at diagnosis) plus a 3D 5 mm margin (but not extending outside the patient) or less (see dose constraints, chapter 5.1.7).

The Planning Treatment Volume 1 (PTV1) is defined as the CTV1 plus a 3D margin depending on the institutional planning values (usually, 5 mm for 3D-CRT/IMRT and 1-5 mm for SRT) to account for day-to day setup variation related to the ability to immobilize the patient and the physiologic motion of the CTV, or less depending on dose constraints (see chapter 5.1.7).

The PTV2 is defined as the CTV2 plus a 3D margin depending on the institutional planning values (usually, 5 mm for 3D-CRT/IMRT and 1-5 mm for SRT) to account for day-to day setup variation related to the ability to immobilize the patient and the physiologic motion of the CTV, or less depending on dose constraints (see chapter 5.1.7).

In patients with no visible tumor (Simpson 1-3), the GTV=CTV should be estimated on the basis of the preoperative imaging demonstrating the meningioma attachment and the information in the surgeon's operative report on tumor attachment and microscopic tumor residue. The centre of the CTV should coincide as accurately as possible with the centre of the dural attachment. The definition of the CTV is at the discretion of the treating radiation oncologist and neurosurgeon.

5.1.3 Treatment planning

Treatment planning CT as well as a post-operative MRI scans are mandatory for (volume-based) 3D treatment plans (3D CRT, IMRT and SRT). Treatment portals will be defined by virtual simulation.

Fusion between the treatment planning CT and the post-operative MRI as obtained shortly before the registration is strongly recommended (see Definition of target volumes, chapter 1.5).

Multi-leaf collimators or secondary collimation with shielding blocks are mandatory in order to ideally conform to the PTV.

Treatment planning should conform to ICRU 50/62 rules for coverage of GTV, CTV and PTV (Ref. 89). Additionally, organs at risk (OAR) should be delineated according to the ICRU 62 rules: brain stem, optic chiasm, both optic nerves, pituitary gland, both eyes and both inner ears (cochleae), whenever appropriate depending on the location of the primary tumor.

5.1.4 Timing of radiotherapy

Treatment with radiotherapy should start within 6 weeks after surgery.

5.1.5 Target dose

Prescription point: Dose prescription for the PTV will be at or near the centre of this volume following recommendations of ICRU 50/62 reports (Ref. 89).

Dose definition: The absorbed dose is specified as Gy.

Tissue heterogeneity: Inhomogeneity correction for bone and soft tissue density variation will be applied.

Prescribed dose and fractionation:

- ◆ The prescribed dose for the CTV is 60 Gy in 30 fractions (Simpson's stages 1-3) or 70 Gy in 35 daily fractions (Simpson's stages 4-5) in one course.
- ◆ Fraction size is 2Gy

- ◆ One fraction given per day, five fractions per week so that overall treatment duration should be 6-7 weeks
- ◆ Dose specification and homogeneity requirements in the PTV (-5% $+7\%$) have to be in accordance with the ICRU guidelines.
- ◆ Interruptions: Patients requiring an interruption in radiotherapy will not receive additional fractions in order to compensate for potential tumor cell repopulation during the treatment gap. (hyperfractionation is not allowed).

5.1.6 Treatment technique

Techniques which allow shielding of normal tissue are encouraged providing they do not compromise treatment of the intended PTV.

Patient position: The patients may be treated in the most appropriate position as long as an optimal fixation can be obtained.

Thermoplastic face mask for 3D CRT and relocable stereotactic frame for SRT is mandatory.

As a minimum to insure correct, reproducible positioning of the patient, orthogonal (AP and lateral) DRRs and corresponding orthogonal portal images (film or electronic) are required.

Field shaping: Shall be done with blocks or multi-leaf collimators which are at least 5 HVL thick.

5.1.7 Normal tissue sparing

It is important to protect OAR whenever possible. Such shielding must be weighted against the possibility of sub-optimal treatment of the target volume. The recommended upper dose limits for different organs are the following:

1. Optic chiasm, optic nerves and tracts should not receive higher (maximum) doses than 60 Gy at 1.8 - 2 Gy/fraction/day (median dose, 56 Gy).
2. The brainstem should not receive higher (maximum) doses than 64 Gy at the surface of this OAR and 54 Gy centrally 1.8 - 2 Gy/fraction/day.
3. The hypothalamus/pituitary should not receive higher (maximum) doses than 56 Gy at 1.8 - 2 Gy/fraction/day. If clinically indicated based on the position of the PTV, the radiation oncologist has the option to relax the hypothalamus/pituitary's dose constraints.
4. The cochlea should not receive higher (maximum) doses than 50 Gy 1.8 - 2 Gy/fraction/day. If clinically indicated based on the position of the PTV, the radiation oncologist has the option to relax the cochlea's dose constraints.

5.1.8 Dose calculation and reporting

Isodose distributions will be calculated through the target in three planes, transverse, coronal and sagittal planes. Recording of integral doses to GTV, CTV PTV and OAR including dose volume histograms is mandatory.

Portal imaging or portal films, if needed using the double exposure technique, will be used for verification.

5.2 Medical concomitant treatments

5.2.1 Concomitant medications

In the case report forms use of corticosteroids, anti-epileptic drug and anti-emetics will specially be recorded with date of start and end of therapy.

5.2.2 Anti-emetics

Prophylactic anti-emetics will be administered at the discretion of the treating physician.

5.2.3 Corticosteroids

Use of corticosteroids around the time of radiotherapy is left to the discretion of the treating physician according to local protocol/custom.

5.3 Expected acute radiation toxicities

Expected toxicities include loss of hair and erythema of the scalp. Reactions in the ear canals or eyes should be observed and treated symptomatically. If significant increase in reaction of the normal tissue occurs, it should be noted and reported to the Study Chairman.

5.4 Treatment interruptions/Treatment withdrawal criteria

Treatment will be delivered daily for all radiation fractions except for weekends. Up to three days of treatment interruptions are permitted for any reason. Interruptions of 3 to 5 treatment days will require notification to the Study Chairman and patients will be regarded as eligible for evaluation. Treatment breaks of more than five treatment days will be considered a protocol violation.

Reasons to terminate protocol treatment before normal completion are:

- ◆ Evidence of disease progression during treatment
- ◆ Unbearable toxicity
- ◆ Patient refusal to pursue the treatment

5.5 Treatment in case of tumor progression

After tumor progression, all further therapy is left at the discretion of the treating physician.

6 Clinical evaluation, laboratory tests and follow-up

6.1 Before treatment start

The following evaluations have to be done:

- ◆ Local histology certifying meningioma WHO grade II or III. Mitotic index and if possible, MIB-1 index and, in women the progesterone/estrogen receptor status.
- ◆ Contrast enhanced pre and post-operative MRI in at least 2 plans. The post-operative MRI brain study should be done within 48 hours of the operation.

- ◆ Complete medical history including medications
- ◆ Physical examination including the performance scale evaluation (WHO performance scales see Appendix B)
- ◆ Mini-Mental Status Examination (MMSE, see Appendix F)

6.2 During the treatment

The patients should be clinical examined weekly during the treatment for:

- ◆ Performance status evaluation (WHO-ECOG)
- ◆ Concomitant medications
- ◆ Acute adverse events scoring according to the National Cancer Institute Common Terminology Criteria for Adverse Events (CTCAE) v.3.0 (<http://ctep.cancer.gov/forms/CTCAEv3.pdf>) grading system.

6.3 During the follow-up

6.3.1 The first follow-up

The first follow-up will be 6 weeks after the last irradiation and will focus on possible acute irradiation toxicity (see table in chapter 6.4). The following evaluation will be performed:

- ◆ Clinical examination, performance status evaluation (WHO-ECOG), interim medical history.
- ◆ Concomitant medications
- ◆ Mini-Mental Status Examination (MMSE, see Appendix F)
- ◆ Acute adverse events scoring according to the National Cancer Institute Common Terminology Criteria for Adverse Events (CTCAE) v.3.0 (<http://ctep.cancer.gov/forms/CTCAEv3.pdf>) grading system.
- ◆ No MRI is requested.

6.3.2 The further follow-up

The next follow-up will be at 6 months after entry on study, then at month 12 and then annually.

Until disease progression, every scheduled follow-up visit includes the following evaluation (see table in chapter 6.4).:

- ◆ Clinical examination, performance status evaluation (WHO-ECOG), interim medical history.
- ◆ Concomitant medications
- ◆ Mini-Mental Status Examination (MMSE, see Appendix F)
- ◆ Late adverse events scoring according to the National Cancer Institute Common Terminology Criteria for Adverse Events (CTCAE) v.3.0 (<http://ctep.cancer.gov/forms/CTCAEv3.pdf>) grading system.
- ◆ Contrast enhanced (gadolinium) MRI (T1, T1 Gado, T2) with slice thickness of 3-5 mm.

After disease progression, the patients will only be followed-up for survival.

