
Treatment
 
Test product, dose and mode of administration
	
The treatment dose will be determined in function of the Simpson's stage.
 
Irrespective of WHO tumor grade patients with Simpson stage 1-3 will receive 60 Gy to the CTV1 and those with Simpson stage 4-5 will be treated with 60 Gy to CTV1 followed by a 10 Gy boost to the CTV2 (total, 70 Gy).
 
Volumes and prescribed dose should be according to the ICRU-50 report.
 
 ◆ GTV: postoperative tumor residual (CT or MRI). ◆ CTV1: GTV and/or subclinical microscopic tumor (may include the pre-operative tumor bed, peritumoral edema, hyperostotic changes if any, and dural enhancement or thickening as seen in the CT/MRI at diagnosis) + 10 mm or less, see dose constraints below. ◆ CTV2: GTV + 5 mm margin or less (see dose constraints, below). ◆ PTV1 & PTV2: CTV1 & CTV2 + 5mm margin (3 mm for stereotactic irradiation). These volumes needed to cover the CTV1 & CTV2 with the 95% isodose line, respectively. 
Fractionation: 2 Gy daily fractions, 5 fractions a week
 
Radiation quality: photon (> 4 MV) beams either conformal, stereotactic, or intensity-modulated radiation therapy (IMRT).
 
Dose constraints (total dose):
 
 ◆ optic pathways: 56 Gy (average); 60 Gy (maximum). ◆ Pituitary gland: 56 Gy. ◆ Brainstem: central, 54 Gy; surface, 64 Gy.
Duration of treatment	The treatment duration is therefore 6 weeks for Simpson's stage 1-3 and 7 weeks for Simpson's stage 4-5.
Reference therapy, dose and mode of administration	Not applicable

Criteria for evaluation
 
Efficacy
 
Safety
	
The primary trial endpoint is the 3-year progression-free survival rate in each stratum of the phase II study.
 
Progression-free survival is counted from entry on study until the first event of either death or progression (as demonstrated by an MRI showing either appearance of new lesions or increased in tumor size by 25% using 3 dimensions)
 
Overall survival is a secondary endpoint and is measured from date of entry to date of death, irrespective of the cause.
 
For both endpoints, the patients not having experienced the event(s) of interest are censored at the date of most recent follow-up.
 
Acute and long term toxicity will be scored according to the NCI-CTCAE version 3.0.
 
Neurological function will be measured by the Mini-Mental Status Evaluation.

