7.1 Tumor progression

The maximum diameters in millimetres will be measured in three perpendicular directions. From this the volume can be calculated by the formula $1/6 \times 3,14 \times \text{length} \times \text{width} \times \text{height}$.

Attributing to possible inaccuracy of volume measurement is the difficulty to delineate the visible extensions due to the gradual transition of tumor into dural hyperaemia. Only clear dural thickening at the distinction of the investigator is to be considered tumor. Merely after a 25% increase of the calculated 3D-volume a decisive event is registered. This volume increase - or tumor recurrence in post-MRI Stage 3 disease - must at least exceed 0.065 cc (this is the volume of a 5mm-diameter sphere) in order to prevent valuation of subtle and possibly false positive tumor growth, as a consequence of 2-3 mm slice thickness and observer bias.

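### The progression floor in section 7.1 is justified by 2-3 mm MRI slices, but section 6.3.2 specifies 3-5 mm slices for follow-up, at which a one-slice reading difference can register a progression

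*Protocol*

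**What the plan says.** Section 7.1 of the protocol defines the imaging event. "The maximum diameters in millimetres will be measured in three perpendicular directions", and an ellipsoid volume is calculated as 1/6 x 3.14 x length x width x height. "Merely after a 25% increase of the calculated 3D-volume a decisive event is registered", and the increase "must at least exceed 0.065 cc (this is the volume of a 5mm-diameter sphere"). The section gives the reason for this floor: to avoid counting subtle, possibly false growth "as a consequence of 2-3 mm slice thickness and observer bias".

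Section 6.3.2 specifies the follow-up scan: "Contrast enhanced (gadolinium) MRI (T1, T1 Gado, T2) with slice thickness of 3-5 mm". It names no imaging plane and does not ask for a constant thickness within a patient. Section 6.1 asks for "Contrast enhanced pre and post-operative MRI in at least 2 plans" before treatment and gives no slice thickness. The protocol summary gives the criterion as "increased in tumor size by 25% using 3 dimensions" and does not mention the floor.

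The 25% rule operates mainly where residual tumour is visible, which is the Simpson 4-5 stratum (section 3.2: "Stage 4 : incomplete excision, macroscopic rest visible (on MRI"; stage 5 is biopsy only). Section 8.1.1.2 tests that stratum against a 3-year PFS of 50%. Section 8.1.1 plans 39 patients for it.

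**The concern.** The protocol names a source of measurement error and sets a safeguard sized for it. It then prescribes images whose slices are as thick as, or thicker than, the upper end of the range the safeguard assumes. Each diameter enters the volume formula as a factor, so an error in one diameter passes in full into the volume. A reading that is one slice longer can therefore exceed 25% in a small residual that has not changed.

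Section 7.1 asks for no confirmatory scan, so a single reading decides the event. A false event counts against 3-year PFS in the Simpson 4-5 stratum. It also ends other data collection for that patient, because section 6.3.2 limits follow-up after progression to survival. Late adverse events and MMSE scores are then lost as well.

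**Working it through.** **Plan's own figures.** For a 5 mm sphere, (3.14/6) x 0.5³ = 0.0654 cc, which reproduces the 0.065 cc floor. For the Simpson 4-5 design with n = 39 and success at 24 or more progression-free patients, the binomial type I error at 50% is 0.0998 and the type II error at 70% is 0.0944. Section 8.1.1.2 states 0.10 and 0.094. Power is 0.906.

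**One-slice error.** Take an unchanged, roughly spherical residual of diameter d (mm), with one diameter read across slices of thickness s (mm). If the later reading is one slice longer:

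- relative increase = s/d, so 25% is reached when d ≤ 4s;
- absolute increase = (3.14/6) x d² x s mm³, which exceeds 65 mm³ when d > √(65 / (0.5233 x s)).

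Both criteria are met in these windows:

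| Slice s | Floor passed from | 25% reached up to | Window |
|---|---|---|---|
| 2 mm | 7.9 mm | 8 mm | 7.9-8 mm |
| 3 mm | 6.4 mm | 12 mm | 6.4-12 mm |
| 4 mm | 5.6 mm | 16 mm | 5.6-16 mm |
| 5 mm | 5.0 mm | 20 mm | 5.0-20 mm |

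Two examples:

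- **d = 10 mm** (volume 0.523 cc): the increase is 20% at 2 mm slices (no event), 30% or 0.157 cc at 3 mm, and 50% or 0.262 cc at 5 mm. The last is about four times the floor (0.262/0.065).
- **d = 20 mm**: the increase is 15% at 3 mm slices (no event) and exactly 25.0% at 5 mm.

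**Effect on the decision (illustration only).** Scans due by three years fall at months 6, 12, 24 and 36, so there are four. Assume a false-progression probability q per scan in a fraction f of patients. Observed PFS is then 0.70 x [1 − f + f(1 − q)⁴], and power is P(X ≥ 24 | n = 39).

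| q | f = 1: PFS, power | f = 0.5: power | f = 0.25: power |
|---|---|---|---|
| 1% | 67%, 0.82 | 0.87 | 0.89 |
| 2% | 65%, 0.72 | 0.83 | 0.87 |
| 3% | 62%, 0.59 | 0.78 | 0.85 |

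Both q and f are assumptions. The protocol gives neither.

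**The case against.** Several counter-arguments have force.

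- **The mechanism is conditional.** It needs a diameter that is read by counting slices. The baseline MRI is in at least two planes, so all three diameters may be readable in-plane. This stands as a condition. It does not remove the point, because section 6.3.2 names no plane for the follow-up scans.
- **Part of the exposure lies within section 7.1's own range.** At 3 mm slices the window is already 6.4-12 mm, so the mismatch did not create that part. What the mismatch adds is the widening to 5-20 mm.
- **Errors also run the other way.** A baseline read one slice too long can hide later true growth. This stands, so the net effect on PFS is not established; only the effect of false progressions has a known direction.
- **The power figures are not tied to slice thickness.** This stands. The rates are assumed, and f = 1 applies them to every patient although the mechanism reaches only residuals inside the window.

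A reader might infer that any residual up to 20 mm is at risk. That is the limit at the thickest permitted slice, where 20 mm lies exactly on the 25% boundary, and below about 5 mm the floor still blocks the event. A reader might also infer that the 25% threshold itself rests on 2-3 mm slices. Section 7.1 attaches that reason only to the 0.065 cc floor.

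**Conclusion.** The contradiction stands. The reason given for the floor in section 7.1 assumes 2-3 mm slices, section 6.3.2 specifies 3-5 mm, and the difference bears on when the primary endpoint is reached. If a diameter is read across slices, the combined criteria leave almost no room for a one-slice false event at 2 mm. They leave diameters of about 6-12 mm exposed at 3 mm and about 5-20 mm at 5 mm.

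The documents do not support a statement that the Simpson 4-5 stratum loses a given amount of power. Without residual sizes or reader error, the number of false events cannot be derived. The illustrated fall from 0.906 to between 0.82 and 0.59 is the case in which every patient is exposed, and it is smaller if only some residuals fall in the window. This is a correction worth making to the endpoint's measurement basis; it does not show that the design fails.

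**What to change.** Reconcile section 6.3.2 with section 7.1 by specifying slices of at most 3 mm, which is the range section 7.1 assumes. Require the same thickness and sequence for a given patient at the post-operative baseline MRI and at every follow-up MRI. Section 6.1 needs a matching line, since it now gives no thickness.

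The cost is a slightly longer acquisition and a change of wording, with no added scan or visit. The change reduces the exposure but does not remove it: at 3 mm, diameters of about 6-12 mm remain open to a one-slice event.

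Keeping 3-5 mm and raising the floor to one slice thickness times the in-plane ellipse area is not a sound alternative. That quantity uses π/4 where the volume formula uses π/6, so it is 1.5 times the one-slice error. At 5 mm slices it would demand growth of 1.5 x 5/20 = 37.5% for a 20 mm residual and 1.5 x 5/10 = 75% for a 10 mm residual. It would override the 25% rule for every residual below 30 mm (1.5 x 5/30 = 25%). That redefines the primary endpoint, delays true progressions and biases PFS upward against the 50% reference.
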